Title of the study: Feasibility study: clinical validation of 3D personalized orthopedic splints in patients with rhizarthrosis.

Product under study: "Bioférula3D", personalized 3D splint classified as a custom-made medical device.

Study population: patients with a new diagnosis of osteoarthritis of the trapeziometacarpal joint (TMJ) (rhizarthrosis).

Sponsor: Optimus 3D, S.L.

[name]
[name]
SPAIN
Phone 1. [name].
Phone 2. [contact]

Study duration: 8 months

Main researcher: [name] [name], PhD

This protocol contains confidential information owned by the Sponsor and the Basque Public Health System

MAIN RESEARCHER: [name]

PROJECT: BIOFERULA3D

LENGTH: 8 months

TITLE:

"Feasibility study: clinical validation of 3D personalized orthopedic splints in patients with rhizarthrosis "

Main objective:

- Evaluate the reduction of pain in patients with regular orthoses compared to the orthosis designed using 3D technology (VAS pain scale)

Secondary objectives:

- Evaluate the functionality between both groups (DASH scale)
- Evaluate patient satisfaction between both groups (6-item scale)
- Subjectively and retrospectively evaluate the time of use between both devices
- Evaluate the strength, using grip and pinch dynamometers

Study subjects: Patients with a new diagnosis of osteoarthritis of the trapeziometacarpal joint (TMJ).

Variables: Pain, functional capacity (DASH), satisfaction, time of use, strength, age, gender, employment status, marital status and educational level.

GENERAL INFORMATION

1. STUDY IDENTIFICATION

Title: Feasibility study: clinical validation of 3D personalized orthopedic splints in patients with rhizarthrosis

Code: BIOFERULA3D

Study design: Randomized prospective follow-up

Product under study: "Bioférula3D", personalized 3D splint classified as a custom-made medical device.

Version and date: Version 5, 10/3/2018

Approved by: CREC (Clinical Research Ethics Committee) from OSI Bilbao Basurto (10/17/2018)

Identification of the promoter and coordinator

Sponsor: Optimus 3D, S.L.

Coordinator: INNOSASUN (BIOEF)

2. ABSTRACT

Osteoarthritis of the hand is a chronic joint disease that usually affects one or more of the finger joints and is a major cause of disability. This affection constitutes one of the main causes of consultation for hand pain. The level of discomfort varies depending on the type of work and the idiosyncrasy of each patient and ranges from slight discomfort and limitations depending on the patient, to notable pain and impediments. In addition to the clinic, radiology is used in the diagnosis and control of evolution. The Eaton-Littler classification (Stages I-II-III-IV) is commonly used.

Treatment of stages I, II, and in some cases stage III, is conservative and is based on pharmacological and rehabilitation measures, including the use of orthoses or splints.

In an ideal situation, these devices should allow freedom of movement and functionality of the hand, being the basis for adequate completion of the treatment (adherence), which could lead to an improvement in pain and functional limitations.

There are currently several types of splints on the market made of temperature-moldable plastic material, a splint that has multiple disadvantages in terms of manufacturing.

Additive manufacturing, frequently associated with the concept of 3D printing, encompasses a set of technologies that is transforming the way of designing and manufacturing application products in many and very diverse sectors. The development of the 3D bio-splint is a project opportunity for a new 3D orthosis that will allow a qualitative leap in the search for an intelligent solution for patients with rhizarthrosis.

Splints developed using this method have a number of advantages both in manufacturing and for patients. Therefore, we proposed a proof-of-concept (feasibility) study. The objectives of this study are exploratory and seek to assess the feasibility of applying a personalized splint compared to a conventional one.

As such, the study tries to find out if the personalized splint can be suitable for the treatment of patients with osteoarthritis of the TMJ and obtain at least similar results, providing greater wearing comfort and facilitating an improvement in the development of the activities of the daily life to patients. Therefore, it is not a design aimed at evaluating the efficacy of such treatment. It is a prospective study with two arms, open with 1: 1 allocation.

The study will be carried out in the outpatient clinics of the OSI Bilbao-Basurto Orthopedic Surgery and Traumatology Service with the collaboration of the Rehabilitation Service.

The study will include a recruitment visit and two follow-up visits, one at a month and another final visit at 3 months. Se incluirán pacientes con nuevo diagnóstico de artrosis de la articulación trapecio-metacarpiana. Patients with a new diagnosis of osteoarthritis of the trapezius-metacarpal joint will be included. One group of patients will wear the usual splint indicated by the Service physicians and the other group the personalized splint designed by the company OPTIMUS 3D.

The main variable is pain, which will be measured, as is usual practice, by a visual analog scale (VAS). In addition, the DASH (Disabilities of the Arm, Shoulder and Hand) questionnaire will be used in its Spanish version (DASHe) and questions about patient satisfaction with the use of splints.

3. JUSTIFICATION

Osteoarthritis of the hand is a chronic joint disease that usually affects one or more of the finger joints and is a major cause of disability (1). In relation to the hand, after the distal interphalangeal joints, the most affected joint is the trapezius metacarpal joint (TMJ) (2).

Rhizarthrosis is defined as a degenerative alteration of the trapezius-metacarpal joint (TMJ) characterized by a progressive deterioration of the articular surfaces and neo bone formation in them

Osteoarthritis of the TMJ is a disease present in a large part of the general population. The symptomatic prevalence is estimated at 6-8% of the population, although its radiological prevalence would be 29-76% depending on the series studied (3). Its diagnosis is basically clinical, although radiological tests are very useful to confirm it and to typify the evolution of the disease.

This affection constitutes one of the main causes of consultation for hand pain. Clinically, patients present pain and decreased functional capacity, which is essentially expressed as a limitation of the range of motion and loss of grip, which generates inability to perform basic activities of life (3).

The TMJ has a great range of mobility, since it basically serves to oppose the thumb to the rest of the fingers and carry out grasping or pinching actions, which is why it is of great use and of great utility in everyday life. This range of movements is favored by being a not very congruent joint, but this fact also explains the tendency to instability, which can lead to abnormal movements between the joint surfaces, which ultimately lead to the development of osteoarthritis of the joint. Over time, a subluxation occurs and the first metacarpal tends to approach the rest of the fingers, producing an adduction. This osteoarthritis leads to pain and functional disability. The pain is usually greater when the joint is stressed, during pinching movements.

The level of discomfort varies depending on the type of work and the idiosyncrasy of each patient and ranges from slight discomfort and limitations depending on the patient, to notable pain and impediments. Besides, the degree of discomfort is usually variable over the years and one can speak of outbreaks of the disease in some cases. Work or professional activity also contributes on the degree of perception of discomfort.

On examination, limitation of joint mobility is observed, so that the degree of excursion of the first metacarpal is limited. Mobility is usually painful. As times goes by, the evolution towards a deformation with a tendency to a progressive subluxation of the first metacarpal over the trapezius is observed. The base of the first metacarpal is displaced to a dorsal subluxation. The head of the metacarpal adducts and the first phalanx hyperextended. This subluxation component adds a worse prognostic factor that influences the choice of treatment.

In addition to the clinic, radiology is used in the diagnosis and control of evolution. The Eaton-Littler classification (4) is commonly used, which proposes 4 stages:

Stage I: normal joint or slight widening

Stage II: Joint narrowing due to cartilaginous wear and osteophytes <2mm

Stage III: Joint narrowing and osteophytes > 2mm

Stage IV: Trapezioscapoid involvement with great trapeziometacarpal narrowing

This radiological classification has therapeutic implications. Although not strictly, in stages III and IV the treatment is fundamentally surgical, with a wide range of proposed techniques, including ligament reconstruction, osteotomy of the base of the first metacarpal, interposition arthroplasty, prosthesis or arthrodesis of the joint (5).

On the other hand, the treatment of stages I, II and in some cases of stage III, is conservative and is based on pharmacological and rehabilitation measures, including functional education and joint hygiene, kinesitherapy, electrotherapy, intra-articular infiltrations and the use of orthoses or splints (6).

However, the mainstay of conservative treatment would be orthotic devices, which have been shown to reduce pain (7). Although there are no clear data to confirm this, it can be assumed that a decrease in pain could be expected to increase functional capacity (8) In an ideal situation, these devices should allow freedom of movement and functionality of the hand, being the basis for adequate treatment completion (adherence), which could lead to an improvement in pain and functional limitations (2).

Despite these facts, there are no guidelines that specify what type of orthosis is best suited for treatment (9). Studies carried out until recently have focused on clinical parameters, being necessary to incorporate other variables such as the perception of the patient, their comfort, which will lead to greater adherence to treatment and, therefore, to improve their pain and functionality.

As mentioned, in the initial treatment for rhizarthrosis, among other measures, a thumb abduction splint is usually prescribed, which seeks to put the thumb in a more physiological position (in

abduction instead of adduction) in which the articular surfaces remain in better relationship, and also seeks to stabilize the joint and relieve it of mechanical demand during daily activities.

The first axis of the hand (Trapezius (carpus) - first metacarpal - proximal and distal phalanges) tilts at the joint between the trapezius and the first metacarpal. It is a very loose joint, allowing a wide range of thumb motion. The most important movement for the functionality of the hand is that of opposition, that is, the one that allows the thumb to pivot until it is placed opposite the rest of the fingers, enabling the pincer function.

When there is a rhizarthrosis or degeneration of the trapezius-metacarpal joint, the greatest pain occurs precisely with the pinching. Biomechanically, the force or pressure exerted with the tip of the finger is transmitted by the lever arm of the aforementioned column, multiplying the mechanical demand at the base of the same, in the trapezius-metacarpal joint. This force can subluxate the joint. Both pressure and subluxation are causes of pain. Therefore, the goal of any orthosis is to immobilize and support this joint.

3.1 Conventional orthoses

Currently there are several types of splints made of temperature-moldable plastic material, a splint that has multiple disadvantages in terms of manufacture:

-Polypropylene shrinks with heat, so it must be taken into account when designing. In addition, special care must be taken when heating and thermoforming it since the orthosis can collapse more easily. If it does not heat up enough, it may not fit well.

-Rectifications cannot be made, so extreme care should be taken with the mold, and it is mandatory to make screeds or modifications before adapting the polypropylene, since once it has been fused, no changes can be made.

Another type of splints that exist on the market are splints made of polyethylene sheets adjustable with velcro. The disadvantage of these splints consists of their instability in immobilization: they do not hold firmly, since they do not fit perfectly to the affected area.

Given that the moments in which the patient has more pain are those in which they are exerting efforts with their hands, there is an increasing tendency to make more ergonomic and smaller models, which even allow wearing gloves on the orthosis if the worker requires it, and plastic materials that can get wet.

Additive manufacturing, frequently associated with the concept of 3D printing, encompasses a set of technologies that is transforming the way of designing and manufacturing application products in many and very diverse sectors. 3D printing is based on the creation of objects, from a computerized file, by superimposing layers of material. 3D printing or additive manufacturing is one of the main axes on which Advanced Manufacturing or Industry 4.0 is based, considered by the European Union as Key Enabling Technology (KET), and therefore, a priority line of action.

The great potential of this technology, as well as its versatility, has made it enter different markets, standing out that of Biosciences-Health. 3D printing allows the custom fabrication of anatomical models for surgical guides, surgical instruments, implants, prostheses, immobilization orthoses, etc. It can be printed on different plastic materials, resin, titanium, other metals, etc. The latest advances in health applications are based on the combination of biology, the creation of biomaterials and 3D printing, evolving to what is known as bioprinting.

Additive manufacturing, within this trend, facilitates the creation of an orthosis fully adapted to the anatomy of each patient. With the design freedom provided by 3D computing tools, the product will be lightened and manufactured in materials that can be wetted.

3.2 Advantages of the 3D orthosis

The development of the 3D bio-splint is a project opportunity for a new 3D orthosis that will allow a qualitative leap in the search for an intelligent solution for patients with rhizarthrosis.

The splints developed using this method have a series of advantages both in manufacturing and for patients, among which we can highlight:

- Increase the precision in the design of the splint to place it in the affected area.
- Reduce the weight of the splint in order to lead a more agile life.
- Improve perspiration.
- Resistance to water, which will improve hygiene, the patient can even bathe with the splint on.
- Greater mobility. The “pincer” movement will not be affected.
- Allow air circulation.
- Improve aesthetic appearance: simple splint design that can be covered if the patient considers it so, for example, with gloves.
- Manufacturing times: the 3D model is made in 3 hours and can be in use by the patient in 72 hours.
- It can be made with fully recyclable materials.

Below is a comparative summary table of the advantages of the 3D orthoses compared to current “conventional” orthoses:

CONVENTIONAL ORTHOSES' ASPECTS TO IMPROVE		ADVANTAGES OF 3D ORTHOSES
Standard orthosis sizes.	Comfort of the affected patient.	-Customized splint adapted to the anatomy of each patient. (Scan to obtain 3D model of affected anatomy and fully customized CAD design).
Thermoplastic Materials / PP / Plastic Cloth (Nylon)	Heavy orthosis. Causes excessive heat and sweating.	-Lightened splint both with the material and its density (possibility to edit the internal density of the material). -The range of materials offered by additive manufacturing will allow testing different materials and considering the most appropriate in terms of their rigidity-flexibility.
PP manufacturing process	Difficulty in manufacturing the PP (see section 3.1.)	-Additional manufacturing is a simple process by which the structure of the orthosis can be manufactured without any problem by melting the plastic and creating the 3D layer by layer. This technique gives total freedom to the design, being able to create pieces unthinkable with other manufacturing methods.
Manufacturing times		Fabrication of an orthosis can be finished in 3 hours approximately.
Usually closed orthosis design	Causes excessive heat and sweating.	-Orthosis design freedom: openings / holes ...
Complete immobilization of the hand	The pitching is affected. The patient cannot perform daily activities	-Immobilization of the trapezius-metacarpal joint but nearly not affecting pitching

3.3 3D bio-splint design (3D orthosis)

Immobilization is the initial treatment for rhizarthrosis, currently carried out using an orthosis or splint made of moldable plastic material or adjustable polyethylene sheets with velcro. These orthoses have a standard size of measurements (2-3 sizes) so they do not adapt to the anatomy of 100% of the patients. In addition, they are splints that cause excessive heat, weight bearing and the impossibility of cleaning or bathing. Due to these reasons, patients tend to fail to follow the immobilization procedure prescribed by clinicians (7-10 hours a day with the splint on).

Faced with this problem, the company OPTIMUS 3D has seen the need to develop a new procedure to treat limb immobilization or orthotic external aid, providing splints with greater comfort and possibly improvement in the completion of the treatment, in addition to a better usability of the splint for the patient. The basic idea of the project is to manufacture the splint adapting it exactly to the physical configuration of the affected hand of the specific patient. The personalized splint will adapt exactly to the dimensions of the affected hand, thereby improving adherence to treatment and minimizing the discomfort derived from the use of standardized splints in sizes.

In patients with rhizarthrosis, the greatest pain appears in the fine and maintained pinch movement. For this reason, the splint should fix the trapezometacarpal joint fully and the metacarpal phalangeal joint partially. The splint will free the movement of the interphalangeal joint thanks to which you can perform daily activities that do not involve much effort. 3D printing will allow a splint design fully adapted to the anatomy of each user.

A scan will be carried out, in the orthopedist's own office, of the possible affected areas that will allow the modeling of anthropomorphic data collection to be carried out using software where a huge cloud of points obtained from the scan of each patient will be modeled. be able to obtain a fabricable 3D model, that is, a design of the bio-technical parameters of the splint, defining and taking into account when designing the custom 3D splint, all the medical and biological aspects necessary to avoid health problems and increase comfort.

OPTIMUS 3D will carry out the engineering and development of the splints using 3D printing technologies.

3.4 Product development: 3D custom splints

- Detailed modeling of the data taken in the scan. Detailed and specific modeling of the data taken by the 3D scanner will be carried out. Using the scanner, a point cloud of the model is obtained, which will be output in .stl format. This .stl file will be exported to a modifiable vector format to be refined and obtain a 3D model of the affected anatomy with which it will be worked later in 3D CAD software.

- Design using 3D software of the models necessary for the manufacture of the prototypes. The design will be made optimally based on the 3D model of the patient obtained in the scan. A design will be created that perfectly fits and wraps the 3D model of the member adjusting the immobilization zones as specified in the load book. Once the orthosis has been designed, it can be exported in STL (stereolithography) format necessary for printing on 3D printing machines. This file is the one that is used as input or input file for 3D printers, it is the digital representation of the model to be printed, from its CAD version. In other words, the STL format (or, failing that, STP. Or IGES. Exportable to STL format) will be necessary to be able to print in 3D. These files can be obtained from various 3D CAD design software. What is needed is to make an export of the digital model that has been built and to worry about saving the file in the necessary format.

4. HYPOTHESIS

3D manufactured orthoses manufactured are effective tools in the conservative treatment of rhizarthrosis in terms of pain reduction.

5. OBJETIVES

The objectives of this study are exploratory since it is a proof-of-concept or feasibility study, which seeks to assess the feasibility of applying a personalized splint compared to a conventional one. We estimate that the clinical results, pain and function of the custom splint will be at least as good as those of conventional splints, but providing greater comfort and satisfaction for the patient.

Main objective

- Evaluate the reduction of pain in patients with usual orthoses compared to the orthosis designed using 3D technology (VAS pain scale)

Secondary objectives

- Evaluate the functionality between both groups (DASH scale)
- Assess patient satisfaction between both groups (6-item scale)
- Subjectively and retrospectively evaluate the time of use between both devices
- Evaluate the strength, using pinch and grip gauges (dynamometers)

6. DESIGN OF THE STUDY

This study is a **proof of concept or feasibility study**. As such, the study tries to find out if the personalized splint can be suitable for the treatment of patients with osteoarthritis of the TMJ and obtain at least similar results, providing greater comfort of use and facilitating an improvement in the development of life activities daily to patients. Therefore, it is not a design aimed at evaluating the efficacy of such treatment.

Prospective study with two arms, open with 1: 1 allocation.

The study will be carried out in the outpatient clinics of the OSI Bilbao-Basurto Orthopedic Surgery and Traumatology Service with the collaboration of the Rehabilitation Service.

The study will include a recruitment visit and two follow-up visits, one after the first month and another final visit at the 3-month period

7. SUBJECTS OF STUDY

Patients with a new diagnosis of osteoarthritis of the trapeziometacarpal joint (TMJ) will be included according to the “recruitment plan” established in Annex III.

Inclusion criteria

- Age between 18 and 75 years
- Clinical diagnosis of rhizarthrosis
- Radiological stage of the classification of Eaton-Littler I/II
- Patients in whom a orthosis or splint is clinically indicated
- Score between 3 and 7 on the VAS pain scale (range 0 to 10)

Exclusion criteria

- Previous treatment of rhizarthrosis
- Refuses to participate in the study
- Disabilities that prevent the completion of the questionnaires
- Severe deformations in the hand
- Presence of other alterations, such as carpal tunnel syndrome, tendinitis, or chronic inflammatory arthropathies

Interventions

One group of patients will wear the usual splint indicated by the staff physicians and the other group the personalized splint designed by the company OPTIMUS 3D.

Patients will be asked to wear the splint for as long as possible, not to disrupt their normal activities (work, household, or otherwise).

Assignment to the treatment branch

Participation in the study will be offered to patients on a consecutive basis. Those patients who meet all the inclusion criteria, none for exclusion and sign the Informed Consent, will be randomized to receive the personalized splint or the control branch (conventional splint). Because the sample size is small and in order to avoid relevant imbalances in the final number of participants in each branch, the sample allocation process will follow a system of randomization by blocks ($n = 4$) and stratified by the level of activity of the patient. This will also try to ensure comparability between the groups in terms of the variable "activity"

Blinding

It does not apply in the present study. It is designed as an open study, since it cannot be blind, neither for patients nor for physicians, due to the fact that one branch will carry splints adapted to each patient and must be prepared by scanning the hand in the consultation itself.

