10. FOLLOW-UP AND DATA COLLECTION

The data will be collected in three visits. The baseline visit, in which the inclusion / exclusion criteria are checked and the corresponding treatment is assigned.

In the control branch, the doctors prescribe the usual splint for each patient. In the intervention branch the personalized splint.

At the baseline visit, the patients will be clinically examined, an X-ray will be taken to verify the inclusion criteria, and the DASH, VAS for pain, and pressure force will be completed.

On the second visit, one month after the splint, pain, satisfaction, DASH, wearing time and grip strength will be evaluated.

At the third follow-up visit (end of the study) that will take place at the third month of follow-up (between 11-14 weeks), patients will complete the DASH questionnaire, the VAS pain scale (from 0-no pain to 10-worse imaginable pain), the pressure force, the time of use and the satisfaction questionnaire made up of 6 items, on an 11-point scoring scale, in which satisfaction will be assessed.

The data of the patients and of the study variables will be collected by the specialists of each of the centers involved in the study. These data will be collected in a data collection notebook and entered into a database designed and adapted for this study.

At the end of the data collection, the errors they may contain will be eliminated by checking logical ranges and detecting impossible codes. Likewise, any errors found will be corrected by checking the clinical history. Once it is considered that the data are refined, they will be closed for statistical analysis.

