11. STATISTIC ANALYSIS

For the descriptive analysis of the quantitative variables, the mean and standard deviation, median and interquartile range will be used. For qualitative variables, frequencies and percentages will be used.

The quantitative variables, pain level and DASH score will be compared, both at baseline and at follow-up, as well as the difference between both moments, as well as time and satisfaction, between the two groups of patients using the T-test of Student or non-parametric Mann-Whitney U test, depending on whether the variables follow a normal distribution or not. The comparison of qualitative variables between both groups, such as gender, marital status, educational level or type of work, expressed as percentages, will be carried out using the Chi-square test or Fisher's exact test.

On the other hand, it will be analyzed within each group of patients if the change in pain and functionality (DASH scale) between baseline and follow-up has been significant or not using the paired t test or the non-parametric Wilcoxon test for data couplets.

Finally, the general linear model will be used to compare the decrease in pain or the improvement in functionality between the two groups of patients, adjusting for pain or baseline functionality. Changes in pain or functionality are considered as the dependent variable of the model, and the group (main independent variable) and the baseline pain or functionality scores as independent.

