Annex III:

Recruitment plan related to patient participation

1. All members of the Orthopedic Surgery and Rehabilitation services will be informed, in the morning session, that initially ALL patients with a first diagnosis of rhizarthrosis in the outpatient clinic must be referred to the Hospital's Outpatient Traumatology Consultations, with symptomatic treatment and with recommendation of relative rest and analgesics. The clinics included are: [name], Rekalde, Deusto, Txurdinaga, Santutxu, Javier Sáenz de Buruaga, Begoña and Bombero Etxaniz.
2. To facilitate the appointment, patients will be referred with PREFERENCE and directed to ORTHOPEDIC SURGERY - RHIZARTHROSIS CLINIC. When doing it in this way, the specific day of the consultation is not given by the administrator of each outpatient clinic, but the request documents are sent by fax to the Hospital's Outpatient Clinics, where the administrators are aware of the study and the days available for citation. In the outpatient clinic, then, the patient receives the information that the appointment will be notified by mail or telephone, and it will take place within a maximum period of 15 days.
3. The administrative staff of the Hospital's Outpatient Clinics will have, each month, at least two consultation spaces for the study of rhizarthrosis, so that no patient waits more than 15 days. These days will be determined with one month in advance, depending on the availability of the doctors, the consultation spaces, and the needs of the service. These inquiries will be notified, also within one month, to the company Optimus 3D. It is not expected to have more than 5 patients each day. The Orthopedic Surgeons who will attend these consultations are doctors [name] and [name]. It is estimated to need about 20 minutes per patient.
4. In the office, it will be determined, from among all the patients, which ones meet all the inclusion criteria and none of the study exclusion criteria. The randomization will be carried out by the Hospital Research Unit. The patients in the experimental group will be scanned the same day of consultation by Optimus 3D company, with the objective of delivering the orthosis as soon as possible, estimating the time from scanning to delivery in 5 working days. Patients who are unable or unwilling to enter the study will be treated according to normal practice.

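### One printed block length of 4 in an open trial lets a fully informed recruiter deduce up to a third of allocations; varied, undisclosed lengths would remove most of that certainty

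*Protocol*

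**What the plan says.** Protocol section 7 (assignment to the treatment branch) states that allocation "will follow a system of randomization by blocks ($n = 4", within strata of activity level. The number of activity levels is not given. The stated reason is the small sample: blocks are used "in order to avoid relevant imbalances in the final number of participants in each branch". The same section says of the study that "it cannot be blind, neither for patients nor for physicians".

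Other parts of the protocol determine who learns what, and when:

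- Section 10 describes "The baseline visit, in which the inclusion / exclusion criteria are checked and the corresponding treatment is assigned". Annex III, item 4, adds that patients allocated to the 3D splint are scanned the same day.
- Annex III, item 3, names two orthopedic surgeons for the study consultations. It does not say how patients are divided between them or whether they share allocations.
- Section 15 has the protocol, and so the block length, reviewed with the investigator and the participating services before the start.

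The protocol also contains safeguards. "Participation in the study will be offered to patients on a consecutive basis", consent comes before randomization, and "The randomization will be carried out by the Hospital Research Unit". Nothing says that block lengths vary or are withheld from the clinic.

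**The concern.** Keeping the list in a separate unit hides the list itself. It does not hide what can be deduced from arms already seen. With a known fixed length and visible past allocations, the end of each block can be worked out before the next patient is entered.

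Eligibility is decided in the consultation and includes clinical judgement, for example whether a splint is indicated or a deformity severe. Someone who knows the next arm could, even unconsciously, enter or defer a patient accordingly. The main outcome is self-reported pain in an unblinded comparison of 20 patients per arm, so even a few selected entries could matter.

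The general linear model in section 11 helps in part by "adjusting for pain or baseline functionality". It would not remove selection on expected wearing time, which section 9 gives as the route by which a more comfortable splint might reduce pain. Section 11 also plans unadjusted comparisons between the groups.

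**Working it through.** The protocol gives no figure for predictability, so there is none to reproduce.

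**Inputs from the protocol.** Block length 4, stratified by activity (section 7); 1:1 and open (section 6); 20 per arm, 40 in total (section 8); two surgeons (Annex III, item 3).

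**Assumptions.** The number of strata, the share *q* of earlier arms that the recruiter knows, and knowledge of the stratum and of the position within the block.

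**Fixed blocks of 4, exact.** A 2:2 block has 6 equally likely sequences. An allocation is certain once both places of one arm are known to be used.

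- Third place: the first two must match (probability 1/3) and both be seen (*q*²), giving *q*²/3.
- Fourth place: the first three always hold two of one arm, and both of these must be seen. This gives *q*³ + 3*q*²(1 − *q*)/3 = *q*².
- Certain share: (*q*²/3 + *q*²)/4 = *q*²/3.

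Results: *q* = 1 gives 33.3%, or 40 × 0.333 = 13.3 patients. *q* = 0.75 gives 18.75%. *q* = 0.5 gives 8.3%, or 3.3 patients.

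**Best guess, all earlier arms known.** The success probabilities for the four places are 1/2, 2/3, 2/3 and 1, so the mean is 2.833/4 = 70.8%.

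**Other splits between two surgeons who do not share.** If one surgeon sees a random fraction *p*, the certain share is (*p*³ + (1 − *p*)³)/3. This is 8.3% at 50/50, 9.3% at 60/40 and 17.3% at 80/20. It is 0% if each sees exactly two patients of every block, and 33% if one surgeon sees whole blocks.

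**Fixed 4 against a random mix of 4 and 6.** These figures come from simulation of 40 patients spread evenly at random over the strata. The predictor knows the set of lengths but not their order. Each cell gives the certain share / best-guess success.

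| Earlier arms known | Strata | Fixed 4 | Mix of 4 and 6 |
|---|---|---|---|
| All | 1 | 33.3% / 70.8% | 5.5% / 68.9% |
| All | 3 | 30.2% / 69.4% | 6.0% / 67.8% |
| All | 6 | 27.2% / 68.1% | 5.7% / 66.1% |
| Three quarters | 1 | 18.8% / 64.7% | 1.4% / 62.4% |
| Half | 1 | 8.4% / 59.9% | 0.2% / 58.5% |
| Half | 6 | 6.8% / 58.8% | 0.7% / 57.8% |

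**Effect on balance (same simulation).** Final difference in arm sizes, mean and 95th percentile:

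| Strata | Fixed 4 | Mix of 4 and 6 |
|---|---|---|
| 1 | 0 and 0 | 0.45 and 2 |
| 3 | 1.09 and 2 | 1.20 to 1.25 and 4 |
| 6 | 1.6 to 1.7 and 4 | 1.8 to 1.9 and 4 |

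The largest possible imbalance within one stratum rises from 2 to 3.

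**The case against.** **The choice is defensible.** Small fixed blocks are an accepted method, and section 7 gives a reason for them. That stands: this is not an error.

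**The change hardly affects guessing.** Someone inclined to select can act on a good guess as well as on certainty. With one stratum, best-guess success falls by 1.9 points (all arms known), 2.3 points (three quarters) and 1.4 points (half). In 40 patients that is 0.8, 0.9 and 0.6 fewer correct guesses. This also stands, and it limits the benefit to the removal of certainty.

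**The percentages rest on facts not in the protocol.** Full knowledge is a ceiling. The 8% needs a random half-and-half split between surgeons who can still count the patients entered in the stratum; without that count it is lower, and other splits give 0% to 33%. Correct, and the figures should be read that way.

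**The protocol already limits the opportunity.** Offers are consecutive, consent precedes allocation, and under Annex III all first diagnoses are referred, with appointments set by hospital administrators within 15 days. Surgeons therefore do not control the order of arrival, which narrows the scope for delay. The safeguards reduce how the knowledge could be used. They do not prevent the deduction, and the judgement on eligibility remains with the clinic.

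**The consequence is small.** Sections 6 and 14 call the study a proof of concept with exploratory comparisons, entry pain is restricted to 3 to 7, and the model adjusts for baseline. This is fair, but the main objective is still a comparison of pain between the arms.

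**Conclusion.** The point holds as a recommended improvement to a defensible design. With a fixed length of 4, up to 33% of allocations (about 13 of 40) are certain to a recruiter who knows the stratum, the block position and all earlier arms. With 2 to 6 evenly filled strata the ceiling is 31% to 27%. Under an assumed random half share for each surgeon it is about 8%, or about 3 of 40.

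A random mix of 4 and 6 brings these down to about 6% and under 1%, while best-guess success barely moves. The effect on the trial's conclusions is likely to be limited. Reporting bias from the open design is a separate matter that this change does not touch.

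**What to change.** In section 7, replace the stated length with wording such as: *permuted blocks of varying length, not disclosed to recruiting staff, within each activity stratum*. The Hospital Research Unit would generate the list, for example with lengths of 4 and 6 in random order, and keep the lengths out of documents that reach the clinic.

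The cost is a new list and a short amendment to a protocol that, according to section 1, already has ethics committee approval; the documents do not show whether recruitment has begun. Balance, the stated purpose of the blocks, becomes slightly worse: the mean final difference in arm sizes grows by about 0.5 patients with one stratum, and by about 0.1 to 0.2 with three to six.
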